## 1. VERSION HISTORY

This statistical analysis plan (SAP) describes the analysis associated with protocol AG348-C-017 Amendment 2 (dated 28-September-2022).

# 2. INTRODUCTION

This SAP provides the detailed methodology for summary and statistical analyses of the data collected in Study AG348-C-017. This document may modify the plans outlined in the protocol; however, any major modifications of the primary endpoint definition or its analysis will also be reflected in a protocol amendment.

The primary clinical study report (CSR) will include all data for each subject up to the end of Double-blind (EODB) Period. The EODB period is defined as the end of the safety follow-up (for subjects who discontinue study treatment during the Double-blind Period) or before the start of study treatment in the Open-label Extension (OLE) Period (for subjects who continue onto the OLE Period after completing the Double-blind Period).

A CSR addendum will include data (associated with objectives that encompass OLE Period evaluations) through the End of Study (EOS). The EOS is defined as the time at which all subjects complete all study visits, are lost to follow-up, have withdrawn consent for further participation in the study, or when the Sponsor terminates the study. Study completion is the date of the last visit of the last subject in the study.

In the following sections, references to "EODB period date/EOS date" are meant to indicate that the EODB period subject-specific dates will be used for analyses to be reported in the primary CSR and the EOS date will be used for analyses to be reported in the addendum CSR.

# **3. OBJECTIVES AND ENDPOINTS**

The study objectives and endpoints are provided in Table 2.

## Table 2:Objectives and Endpoints

Primary Objective	Primary Endpoint				

 
To compare the effect of mitapivat versus placebo on anemia in subjects with α- or β-non-transfusion dependent thalassemia (NTDT)
 
	
 
Hemoglobin (Hb) response, defined as a ≥1.0 g/dL increase in average Hb concentration from Week 12 through Week 24 compared with baseline
 
				
Key Secondary Objectives	Key Secondary Endpoints				
• To compare the effect of mitapivat versus placebo on fatigue	• Change from baseline in average Functional Assessment of Chronic Illness Therapy (FACIT) -Fatigue subscale score from Week 12 through Week 24				
• To compare the effect of mitapivat versus placebo on additional measures of anemia	• Change from baseline in average Hb concentration from Week 12 through Week 24				
Secondary Objectives	Secondary Endpoints				
• To evaluate the effect of mitapivat versus placebo on anemia and markers of hemolysis and erythropoiesis	• Hb 1.5+ response, defined as a ≥1.5 g/dL increase in average Hb concentration from Week 12 through Week 24 compared with baseline				
	• Change from baseline in indirect bilirubin, lactate dehydrogenase (LDH), and haptoglobin at Week 24				
	• Change from baseline in reticulocytes and erythropoietin at Week 24				
• To evaluate the effect of mitapivat versus placebo on additional measures of fatigue	• Improvement in the Patient Global Impression of Severity (PGIS) -Fatigue by at least 1 category at Week 12, 16, 20, and 24 compared with baseline, or "no change" if no or mild fatigue at baseline				
	• Improvement in the Patient Global Impression of Change (PGIC) -Fatigue at Week 12, 16, 20, and 24, or "no change" if no or mild fatigue at baseline				
• To evaluate the effect of mitapivat versus placebo on physical activity	• Change from baseline in the 6-minute walk test (6MWT) distance at Week 24				
• To evaluate the effect of mitapivat versus placebo on iron metabolism	• Change from baseline in markers of iron metabolism, including serum ferritin and transferrin saturation at Week 24				
• To evaluate the safety of mitapivat	• Type, severity, and relationship of adverse events (AEs) and serious adverse events (SAEs)				
• To evaluate the PK and PD effects of mitapivat	• Plasma or blood concentrations and PK parameters of mitapivat and PD parameters, including adenosine triphosphate (ATP) and 2,3-diphosphoglycerate (2,3-DPG)				

[figure not shown]

[figure not shown]
a Analyses associated with this objective will be described in a separate SAP.

## 4. STUDY DESIGN

This is a Phase 3, double-blind, randomized, placebo-controlled, multicenter study evaluating the efficacy and safety of mitapivat versus placebo in adult subjects with  $\alpha$ - or  $\beta$ -NTDT followed by an OLE Period. Approximately 171 subjects are planned to be randomized in this study. This multicenter study will be conducted internationally.

An overview of the study design is presented in Figure 1.

Abbreviations: BID = twice daily; EOS = End of Study.

# 5. ANALYSIS DATA SETS

The following analysis data sets will be evaluated and used for presentation of the data:

Population	Description		
All Screened Subjects	All subjects who sign the informed consent form (ICF).		
Full Analysis Set (FAS)	All subjects who are randomized. Subjects will be classified according to the randomized treatment arm according to the intent-to-treat (ITT) principle. The FAS is the primary analysis set for the evaluation of efficacy endpoints, unless otherwise specified.		
Per-Protocol Set (PPS)	The PPS is a subset of the FAS. Subjects who meet any of the following criteria will be excluded from the PPS:		
	• Do not receive at least 1 dose of the randomized treatment		
	• Do not meet Inclusion Criterion #2 (ie, do not have documented thalassemia)		
	• Do not meet Inclusion Criterion #3 (ie, Hb concentration >10.0 g/dL based on an average of at least 2 Hb concentration measurements [separated by ≥7 days] collected during the Screening Period)		
	• Do not meet Inclusion Criterion #4 (ie, do not meet criteria for NTDT)		
	• Meet Exclusion Criterion #3 (ie, prior exposure to gene therapy or prior bone marrow or stem cell transplantation)		
	• Meet Exclusion Criteria #4 or #5 (ie, currently receiving treatment with luspatercept or hematopoietic stimulating agents)		
Safety Analysis Set	All subjects who receive at least 1 dose of study treatment. Subjects will be classified according to the treatment received. If a subject randomized to placebo receives at least 1 dose of mitapivat in the Double-blind Period, then the subject will be classified to the mitapivat arm.		
Open-label Extension (OLE) Analysis Set	All subjects who receive at least 1 dose of open-label mitapivat after the Double-blind Period.		
Pharmacokinetic (PK) Analysis Set	A subset of the safety analysis set including all subjects with at least 1 mitapivat plasma concentration measurement $\geq$ LLQ.		
Pharmacodynamic (PD) Analysis Set	A subset of the safety analysis set including all subjects with at least 1 blood 2,3-DPG or ATP concentration measurement $\geq$ LLQ.		
PK/PD Analysis Set	A subset of the PK analysis set including all subjects in the PK and PD analysis sets, with at least 1 time-matched ATP or 2,3-DPG concentration to a mitapivat plasma concentration.		

Abbreviations: 2,3-DPG =2,3-diphosphoglycerate; ATP = adenosine triphosphate; ICF = informed consent form; ITT = intent-to-treat; LLQ = lower limit of quantification.

Table 3 summarizes the use of the analysis sets.

Endpoints	FAS	PPS	Safety Analysis Set	OLE Analysis Set	PK Analysis Set	PD Analysis Set	PK/PD Analysis Set
Demographic and other baseline characteristics	~			✓			
Disposition	✓			✓			
Major protocol deviations	~			~			
Exposure and concomitant therapies			~	√			
Efficacy	~	
 
✓ (primary and key secondary only*)
 
		~			
Safety			✓	~			
РК					✓		
PD						✓	
PK/PD							✓

Table 3:Analysis Data Sets for Each Endpoint

\* Key secondary endpoints are defined in Section 7.6.2.

Abbreviations: FAS = full analysis set; OLE = open-label extension; PD = pharmacodynamic; PK = pharmacokinetic; PPS = per-protocol set.

# 6. GENERAL STATISTICAL CONSIDERATIONS

## 6.1. Randomization, Blinding, and Unblinding

Eligible subjects will be randomized in a 2:1 ratio to mitapivat or matched-placebo.

Randomization assignment will be implemented by an interactive voice/web response system (IXRS) and stratified by:

- Baseline Hb concentration ( $\leq 9.0 \text{ g/dL}$  or 9.1-10.0 g/dL)
- Thalassemia genotype (α-thalassemia/HbH disease or β-thalassemia)

This study includes a Double-blind Period followed by an OLE Period. Study subjects, Investigators, clinical study center personnel, pharmacists, and the Sponsor will be blinded to the subject's treatment assignment. After completing the Double-blind Period, subjects will be provided the opportunity to receive mitapivat in the OLE Period. At the last study visit of the Double-blind Period, subjects who continue in the OLE Period will be provided with active mitapivat; however, study subjects, Investigators, clinical study center personnel, and the Sponsor will continue to remain blinded to the randomized treatment assignment during the previous Double-blind Period until the study is unblinded for the analysis of the primary endpoint.

## 6.2. Sample Size Determination and Decision Rules

#### 6.2.1. Sample Size Determination

The following statistical hypothesis will be tested to address the primary objective:

 $H_{01}$ :  $p_{t1} - p_{c1} = 0$  vs  $H_{11}$ :  $p_{t1} - p_{c1} \neq 0$ 

where  $p_{t1}$  and  $p_{c1}$  are the proportion of subjects with a Hb response in the mitapivat arm and placebo arm, respectively.

Assuming an Hb response rate of 10% in the placebo arm, 171 subjects (114 subjects randomized to mitapivat and 57 subjects randomized to placebo) are needed to provide a 95% power to detect an increase in Hb response rate from 10% in the placebo arm to 35% in the mitapivat arm based on a 2-sided significance level of 0.05.

Given the large variability of Hb concentration in patients with anemia, the SD of change from baseline can be as high as 1.3 g/dL (Kalantar-Zadeh and Aronoff, 2009). Assuming no changes in Hb concentration in subjects receiving placebo, approximately 10% of subjects could achieve an Hb response simply because of the variability in Hb concentration measurements. Therefore, a 10% Hb response rate is being assumed for the placebo arm.

The assumption of a 35% Hb response rate was informed by the results from Study AG348 C-010. As of 20 August 2020, 70% (14/20 overall, 10/15 in those with  $\beta$ -thalassemia, and 4/5 in those with  $\alpha$ -thalassemia) subjects achieved a  $\geq 1.0$  g/dL increase in average Hb concentration from Week 12 through Week 24 compared with baseline. Considering a more heterogeneous population in this large, double-blind, Phase 3 study and a commonly noted decrease in efficacy between Phase 2 and Phase 3 studies, a 35% response rate for mitapivat arm is deemed to be a reasonable assumption.

Additionally, the following statistical hypotheses will be tested to address the key secondary objectives:

```
\begin{split} H_{02}: \mu_{t1} - \mu_{c1} &= 0 \ \text{vs} \ H_{12}: \ \mu_{t1} - \mu_{c1} \neq 0 \\ H_{03}: \mu_{t2} - \mu_{c2} &= 0 \ \text{vs} \ H_{13}: \ \mu_{t2} - \mu_{c2} \neq 0 \end{split}
```

where

- $\mu_{t1}$  and  $\mu_{c1}$  are the mean change from baseline in average FACIT-Fatigue subscale score from Week 12 through Week 24 in the mitapivat arm and placebo arm respectively
- μt2 and μc2 are the mean change from baseline in average Hb concentration from Week 12 through Week 24 in the mitapivat arm and placebo arm, respectively

The sample size of 171 subjects will also provide 80% power at a 2-sided significance level of 0.05 to detect a 5.5 difference in the change from baseline in average FACIT-Fatigue subscale score from Week 12 through Week 24 between the mitapivat arm and the placebo arm. These calculations assume a change from baseline in average FACIT-Fatigue subscale score from Week 12 through Week 24 in the mitapivat arm of 4.5 and in the placebo arm of -1 and a common standard deviation (SD) of 12.

Assumptions of the FACIT-Fatigue score change from baseline are from several sources. FACIT-Fatigue results from placebo-controlled studies in NTDT have not yet been published. The available literature and feedback from the thalassemia experts suggest an increase of 3 points in FACIT-Fatigue score for every 1 g/dL increase in Hb. Results of the open-label luspatercept NTDT study with similar eligibility criteria included mean FACIT-Fatigue score change from baseline to Week 24 of approximately +2.8 (N=17) and mean Hb change from baseline to Week 24 of approximately +1.2 g/dL (N=~25) (Piga et al, 2016). In a recent randomized, open-label, controlled trial in paroxysmal nocturnal hemoglobinuria, the observed FACIT-Fatigue score change from baseline to Week 16 was +9.2 in the pegcetacoplan treatment arm, and Hb change over the same period was +2.4 g/dL (N=41 patients randomized) (Hillmen et al, 2020). Based on the Hb data observed in the Phase 2 Study AG348-C-010 and these results from trials, an increase in the FACIT-Fatigue score of approximately +4.5 in the mitapivat arm over Weeks 12 to 24 and a small decrease in the score of -1 in the placebo group are expected, with an estimated SD of 12 for the difference of changes.

Overall type I error will be maintained at or below 2-sided  $\alpha$ -level of 0.05 by a fixed -sequence testing procedure (Westfall and Krishen, 2001). H01 will be tested first; if H01 is rejected, then H02 will be tested; if H02 is rejected, then H03 will be tested. All tests will be conducted at the 2-sided 0.05 significance level.

## 6.2.2. Decision Rules

The study will have demonstrated that mitapivat is statistically significantly superior to placebo for Hb response if the 2-sided p-value for the test of the difference in the Hb response rate is  $\leq 0.05$  and the Hb response rate is higher for the mitapivat arm than for the placebo arm.

To protect the integrity of the study and to preserve the type I error at or below 2-sided  $\alpha$ =0.05, the testing strategy outlined in Section 6.2.1 will be followed and statistical significance will be achieved for mitapivat compared to placebo for each key secondary endpoint that can be tested per this strategy at the associated significance level.

## 6.3. Definitions

## 6.3.1. Study Drug and Study Treatment

In the Double-blind Period, both study drug and study treatment are defined as mitapivat or matched placebo.

In the OLE Period, both study drug and study treatment are defined as mitapivat.

#### 6.3.2. Start and End Dates of Study Treatment

The start of study treatment is the earliest date/time of administration of a non-zero dose of the study drug.

The end of study treatment is the latest date/time of administration of a non-zero dose of the study drug on or before the EODB period date/ EOS date.

#### 6.3.3. Study Day

The study day for assessments or events occurring on or after the start of study treatment (eg, AE onset, disease assessment) will be calculated as:

Study day=Date of the assessment or event-start of study treatment+1.

The study day for assessments or events occurring before the start of study treatment (eg, baseline characteristics, medical history) will be negative and calculated as:

Study day=Date of the assessment or event-start of study treatment.

There is no study day 0. The study day will be displayed in data listings.

#### 6.3.4. Baseline

#### 6.3.4.1. Double-blind Period

Throughout the SAP for analyses based on the Double-blind Period, 'reference date' will be used to refer to randomization date for subjects randomized and not dosed, or the start of study treatment for subjects randomized and dosed.

#### Efficacy Evaluations

For markers of iron metabolism (Section 7.6.3.5), markers of hemolysis and erythropoiesis (Section 7.6.3.2),

baseline is defined

as the average of all assessments within 42 days before the 'reference date'. Assessments collected within 8 weeks after an RBC transfusion will be excluded from the baseline derivation for these efficacy parameters and for endpoints associated with measures of fatigue. Baseline will be derived based on central laboratory data; if no central laboratory data are available, then local laboratory data will be used to derive the baseline.

For other efficacy endpoints baseline is defined as the last assessment before the 'reference date'.

#### **Demographic and Other Baseline Characteristics**

For summaries of demographic and other baseline characteristics based on the FAS, baseline is defined as the last assessment before the 'reference date'.

#### **Safety Evaluations**

For clinical laboratory assessments the following applies:

- Before deriving the baseline:
  - If there are multiple records with the same assessment day and time from the same laboratory, the average value will be used.
  - If there are multiple records with the same assessment day and time from different laboratories, the value from the central laboratory will be used.
- The baseline will then be the last value before the start of study treatment.

For all other safety parameters, the last assessment before the start of study treatment will be used as the baseline.

#### **PD** Evaluations

The baseline is defined as the pre-dose whole blood concentration of 2,3-DPG and ATP on study day 1. If this concentration is <LLQ, baseline will be set to missing.

If, per protocol, an assessment is to be performed on study day 1, before the first dose of study treatment, and the assessment time, time of first dose of study treatment, or both are missing or not collected, it will be assumed that the assessment is performed before the first dose of study treatment. Unscheduled assessments will be used in the determination of baseline; however, an unscheduled assessment on study day 1 for which the time relative to start of study treatment cannot be determined, will be considered to have been obtained after administration of study treatment.

If no assessment meets the definition of baseline for an evaluation, the baseline will be set to missing.

#### 6.3.4.2. Open-label Extension Period

For subjects randomized to mitapivat, the baseline for all assessments in the OLE Period will be that derived in the Double-blind Period (Section 6.3.4.1).

For subjects randomized to placebo, the baseline is derived following the same rules as for the Double-blind Period but using start of mitapivat in the OLE Period instead of randomization date or 'reference date'.

Age at baseline will be calculated based on the date of informed consent for the study as described in Section 6.4.2.

In addition, for evaluations that are unique to the OLE Period (bone mineral density [BMD] by DXA [Section 7.7.5], baseline is derived as the last assessment before first dose of study treatment (mitapivat or placebo).

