5.1. Inclusion Criteria

Subjects are eligible to be included in the study only if all the following criteria apply:

- 1. ≥ 18 years of age at the time of providing informed consent.
- 2. Documented diagnosis of thalassemia (β -thalassemia with or without α -globin gene mutations, HbE/ β -thalassemia, or α -thalassemia/HbH disease) based on Hb electrophoresis, Hb high-performance liquid chromatography, and/or DNA analysis from the subject's medical record. If this information is not available from the subject's medical record, the test(s) can be performed by a local laboratory during the Screening Period. If a local laboratory is unable to perform the test(s), results from the comprehensive α and β -globin genotyping performed by the study central laboratory can be used (see Section 8.2 and Section 8.9).
- Hb concentration ≤10.0 g/dL (100.0 g/L), based on an average of at least 2 Hb concentration measurements (separated by ≥7 days) collected during the Screening Period.
- 4. Non-transfusion dependent, defined as: ≤5 RBC units during the 24-week period before randomization **and** no RBC transfusions ≤8 weeks before providing informed consent **and** no RBC transfusions during the Screening Period.
- 5. If taking hydroxyurea, the hydroxyurea dose must be stable for ≥16 weeks before randomization.
- 6. Women of childbearing potential (WOCBP) must be abstinent of sexual activities that may result in pregnancy as part of their usual lifestyle or agree to use 2 forms of contraception, 1 of which must be considered highly effective, from the time of providing informed consent, throughout the study, and for 28 days after the last dose of study drug. The second form of contraception can be an acceptable barrier method (see Appendix 2 for the definition of WOCBP and acceptable contraception methods).
- 7. Written informed consent before any study-related procedures are conducted and willing to comply with all study procedures for the duration of the study.

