6.6.2. Permitted Concomitant Therapy

Transfusions and other supportive care therapies are permitted as clinically indicated, unless otherwise specified in Section 6.6.3. Concomitant administration of iron chelation therapy will be recorded on the eCRF. Red blood cell transfusions are discussed in Section 8.7.

Initiation of new Herbal/dietary supplements (HDS) is permitted only after discussion with the Investigator.

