8.7. Red Blood Cell Transfusions

All HRQOL assessments and the 6-minute walk test (6MWT) (see Section 8.11) must be conducted before all other study visit assessments, including blood sampling. All blood samples must be collected before administration of the study drug and before the RBC transfusion, if an RBC transfusion is scheduled on the same day.

Transfusion history will be recorded for the 24-week period before randomization. On-treatment transfusions will also be recorded. The transfusion history and on-treatment transfusion record includes transfusion dates, number of RBC units transfused, and pretransfusion Hb concentration. An RBC unit refers to packed red blood cell (pRBC) preparations. Due to hematocrit concentration differences in blood products used per local standards of care, 2 units of whole blood are equivalent to 1 unit of pRBCs and constitute an RBC unit. If available, the volume and the hematocrit of each transfused RBC unit should also be recorded. All RBC transfusions, including those received outside of the clinical study center, must be recorded.

Subjects may receive RBC transfusions at the discretion of the Investigator as clinically indicated.

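### One late double-blind transfusion can leave a placebo subject with no open-label baseline for an averaged laboratory marker

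*SAP*

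**What the plan says.** SAP 6.3.4.2 keeps the Double-blind baseline for subjects randomized to mitapivat. The placebo arm gets a different rule: "the baseline is derived following the same rules as for the Double-blind Period but using start of mitapivat in the OLE Period".

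The rules carried over are in SAP 6.3.4.1. Laboratory markers of three kinds (iron metabolism, hemolysis, erythropoiesis) have their baseline calculated, in the SAP's words, "as the average of all assessments within 42 days before the 'reference date'. Assessments collected within 8 weeks after an RBC transfusion will be excluded". The closing rule of that section reads: "If no assessment meets the definition of baseline for an evaluation, the baseline will be set to missing". Other efficacy endpoints use the last assessment, with no 42-day limit. Safety laboratory tests use the last value, with no transfusion exclusion.

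At study entry, Protocol 5.1 (inclusion criterion 4) requires no transfusion in the 8 weeks before consent and "no RBC transfusions during the Screening Period". During treatment the position differs: "Transfusions and other supportive care therapies are permitted as clinically indicated" (Protocol 6.6.2), and Protocol 8.7 leaves the decision to the Investigator.

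**The concern.** The exclusion lasts 56 days and the look-back 42, so a single transfusion can remove every value eligible for the baseline. At the Double-blind baseline this cannot happen to an eligible subject, because the entry criteria keep the preceding weeks free of transfusion. At OLE entry that protection is gone, and the same rule can take effect.

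Only placebo subjects crossing to mitapivat can lose a baseline this way. The OLE is where their response to first exposure is described. A missing baseline removes the subject from every later OLE change for that marker, and the subjects removed are selected by having needed a transfusion. For most of the markers a usable value from before mitapivat exists but falls outside the window.

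**Working it through.** **Inputs**
- Look-back 42 days, exclusion 8 × 7 = 56 days (SAP 6.3.4.1).
- First open-label dose on the evening of the Week 24 visit, so the Week 24 sample precedes it (Protocol Table 1, study drug footnote).
- Samples on a transfusion day are drawn before the transfusion (Protocol 8.7).
- Sampling (Protocol Table 1): hematology, liver tests and LDH every 4 weeks; erythropoietin and haptoglobin on Day 1 and at Weeks 12 and 24; iron panel on Day 1 and at Week 24.
- 57 placebo subjects (Protocol 10.2).

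**Calendar.** The SAP's target-day formula, 1 + 7 × week, gives Day 85 (Week 12), 113 (Week 16), 141 (Week 20) and 169 (Week 24), matching Protocol Table 1. The look-back runs from 169 − 42 = Day 127 to Day 169. Week 20 is inside it. Week 16, at 169 − 113 = 56 days back, is not.

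**Which transfusion days empty the baseline.** A sample on day v is dropped after a transfusion on day T if 0 < v − T ≤ 56.

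| Markers | Scheduled samples in Days 127-169 | T that leaves none | Days |
|---|---|---|---|
| Ferritin, transferrin saturation, erythropoietin, haptoglobin | Week 24 | 113-168 | 56 |
| LDH, indirect bilirubin, reticulocytes | Weeks 20 and 24 | 113-140 | 28 |

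For the second group, a transfusion on Days 141-168 leaves Week 20 usable, unless that visit was missed. Moving visits by ±4 days changes the 28 days to between 20 and 36. Hb belongs in the second group if it follows the averaged baseline of Protocol 10.4.1.1; the 44-day look-back given there for dosed subjects yields the same days.

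**Two example records**
- Transfusion on Day 125: Week 20 is 141 − 125 = 16 days later and Week 24 is 169 − 125 = 44 days later. Both are dropped and Week 16 is outside the window, so all the averaged markers lose their baseline.
- Transfusion on Day 150: Week 24 is 169 − 150 = 19 days later and is dropped. The Week-24-only markers lose their baseline. LDH, indirect bilirubin and reticulocytes keep Week 20.

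**Size.** Assume one transfusion, uniform over Days 2-168 (167 days). The share that empties the baseline is 56/167 = 33.5% for the first group and 28/167 = 16.8% for the second. A simulation with visits varied by ±4 days gives 33.2% and 16.9%. The documents give no transfusion rate, so a range is assumed:

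| Placebo subjects with one transfusion | First group | Second group |
|---|---|---|
| 5% (57 × 0.05 = 2.85) | 2.85 × 0.335 = 1.0 | 2.85 × 0.168 = 0.5 |
| 10% (5.7) | 1.9 | 1.0 |
| 20% (11.4) | 3.8 | 1.9 |

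**The case against.** The best reply is that the effect is narrow and that missing is a defensible choice. Much of this stands.

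- **Scope.** A reader might infer that the subject leaves every OLE change-from-baseline result. The documents do not support that. Fatigue and 6-minute walk baselines use the last assessment without a 42-day limit, and DXA uses the last one before first study treatment. Safety laboratory baselines ignore transfusions. Protocol Table 10 places reticulocytes under hematology and indirect bilirubin and LDH under liver tests, so those three may still appear in the OLE safety summaries of SAP 7.7.3. The other four markers are not in that table.
- **Duration.** Nor is the loss a five-year one for every marker. Erythropoietin and haptoglobin have scheduled OLE draws only at Weeks 36 and 48, plus erythropoietin at Safety Follow-up. The iron panel does run to Week 288.
- **Who is lost.** It is tempting to say the most anemic subjects. Protocol 2.1.1 ties transfusion in this disease to events such as infection, pregnancy, surgery and aplastic crisis, so only selection by need for transfusion is supported.
- **Rescue.** Unscheduled samples count toward baseline, as do local values when no central value exists.
- **Hidden text.** The SAP's baseline sentence has a gap and Section 7.11 is not visible, so a fallback could exist there. The visible marker sections describe summaries only through Week 24, although SAP Table 3 assigns efficacy to the OLE Analysis Set. The exact OLE outputs affected therefore cannot be listed.
- **Old baselines.** For ferritin and transferrin saturation, the only earlier scheduled value is Day 1, 168 days before OLE start. Using it would credit the placebo period's change to mitapivat.

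None of this removes the central point: in the visible text, a usable Week 12 or Week 16 value is set aside for want of a fallback.

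**Conclusion.** The point holds for the averaged markers only. One permitted transfusion on about Days 113-168 (Week-24-only markers) or Days 113-140 (4-weekly markers) sets the OLE efficacy baseline to missing and removes the subject from that marker's OLE change results.

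The expected loss is about 0.5 to 4 of 57 placebo subjects per marker. This assumes a 5-20% chance of a single transfusion spread evenly over the period, all 57 entering the OLE, and no rescuing unscheduled sample. Fewer entrants or rescued baselines would lower the figure; repeat transfusions would raise it.

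This is a minor improvement to an addendum report. It has no bearing on the primary or key secondary analyses, which use Double-blind data and baselines.

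**What to change.** Add a fallback to SAP 6.3.4.2 for placebo subjects. If transfusion has excluded every assessment in the 42 days before the first OLE dose, use the most recent assessment that was taken after the first double-blind dose, before the first OLE dose, and not within 8 weeks after a transfusion. Flag such baselines in the outputs. The value will typically be Week 16 for LDH, indirect bilirubin and reticulocytes, and Week 12 for erythropoietin and haptoglobin. Anchor the rule on the first dose: randomization may precede it by up to 48 hours, so a rule tied to randomization could admit the Day 1 sample.

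For ferritin and transferrin saturation, leave the baseline missing in the main summary and show results with the Double-blind baseline only as a flagged sensitivity summary.

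Simply lengthening the look-back is a weaker remedy. At target visit days, 56 days would cover the 4-weekly markers and 84 days would be needed for erythropoietin and haptoglobin. The iron panel would need 168 days, which reaches Day 1.

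The cost is a short SAP addition and a derivation flag. The downside is an older, single-value baseline for a few subjects, mixed with more recent baselines for the rest.
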